9. RESEARCH DESIGN AND METHODS

Study Design:

This will be a randomized, prospective clinical trial. All patients enrolled will undergo echocardiographic evaluation with AV delay optimization which will be compared to intrinsic conduction, and thus patients will serve as their own controls with respect to the acute hemodynamic data.

After observing the acute hemodynamic effects of AV delay optimization vs. intrinsic conduction, patients will be randomized in a 1:1 ratio by order of enrollment to either the echocardiographically optimized AV delay vs. with a long fixed AV delay allowing for intrinsic conduction. All patients will then get follow up echocardiograms at 6 months after randomization to assess if there are any remodeling changes associated with a higher burden of RV pacing. Patients will be monitored for any adverse events with routine clinic visits one-two weeks after implantation and programming and at 3 month intervals or as needed as per standard of clinical care.

Methods:

Patients who have AV conduction with long PR intervals (>230 msec) with preserved LV function who are receiving dual chamber pacemakers for symptomatic bradycardia will be evaluated by echocardiography evaluating baseline systolic and diastolic function as well as for mechanical dyssynchrony. Baseline aortic TVI, as a surrogate of cardiac output, will be measured and will be compared with aortic TVI with AAI pacing at 70 bpm and 90 bpm and with DDD pacing 70 bpm and 90 bpm at the optimal AV delay achieved with atrio-ventricular pacing at each heart rate.

To determine the optimal AV delay, the bradycardia device will be programmed to the DDD mode, and all patients will undergo echocardiographic analysis at varying AV delays. Measurement of continuous-wave aortic Doppler flow velocities in the apical five chamber view at baseline and at eight AV intervals: 220, 200, 180, 160, 140, 120, 100, 80 ms. will be done. After 20 cardiac cycles at each AV delay, measurements will be made on the final three to four cardiac cycles and averaged. The optimal AV delay will be defined as the AV delay associated with the largest average aortic Doppler VTI.

Measurements of diastolic dysfunction and dyssynchrony will also be re-evaluated with AAI pacing and with DDD pacing at optimized AV delays to evaluate the effects of pacing on these parameters as well.

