10. HUMAN SUBJECTS

A total of 40 patients will be recruited from the Cardiology Electrophysiology clinics of either gender for Echocardiography and AV delay optimization.

Inclusion Criteria: (all must be met)

1. Must have Symptomatic bradycardia requiring dual chamber pacemaker

2. PR interval of > 230 msec
3. Must give written informed consent
4. Must be at least 18 years old

Exclusion Criteria: (presence of any one or more)

1. Complete or high grade AV block
2. Persistent Atrial Fibrillation

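### The order of testing AV delays and pacing modes is neither stated nor randomized, so session drift could be confounded with AV delay and with AAI versus optimized DDD if conditions are tested as listed

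*Protocol*

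**What the plan says.** Protocol section 9 (Study Design) states that "patients will serve as their own controls with respect to the acute hemodynamic data". The Methods part of that section sets out the acute comparison as baseline against "aortic TVI with AAI pacing at 70 bpm and 90 bpm and with DDD pacing 70 bpm and 90 bpm at the optimal AV delay", with the optimum found separately at each rate. The sweep covers "eight AV intervals: 220, 200, 180, 160, 140, 120, 100, 80 ms". At each setting, "After 20 cardiac cycles at each AV delay, measurements will be made on the final three to four cardiac cycles and averaged". The selection rule is: "The optimal AV delay will be defined as the AV delay associated with the largest average aortic Doppler VTI".

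The only randomization is of the later programming arm: "After observing the acute hemodynamic effects of AV delay optimization vs. intrinsic conduction, patients will be randomized in a 1:1 ratio by order of enrollment". Section 9 states no acquisition order for the delays or the modes. It describes no random or counterbalanced order, no reversed sweep and no return to a reference setting. The SAP has no order or period term. Its paired test is described for baseline against 6 months, and no test is named for the acute AAI versus DDD comparison.

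**The concern.** A within-patient comparison removes differences between patients. It does not remove changes over time within the session, such as a moving probe position, changing loading, or the patient settling. Only the order of testing, or bracketing with repeat readings, protects against those.

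Two results depend on the session. The sweep maximum sets the delay that is then programmed in the optimized arm. The difference between AAI and optimized DDD answers the first specific aim. The optimized DDD delay cannot be known until the sweep at that rate is complete. If AAI is recorded once, before the sweep, AAI always comes first and DDD later. A drift with the same direction in most patients would then look like an effect of delay or mode, and enrolling more patients would not average it out. The SAP contains nothing that could separate the two.

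**Working it through.** **No figure to reproduce.** The plan gives no drift, no VTI variability, and no effect size or power behind its statement that "A total of 40 patients will be recruited". Everything below on drift and SD is assumed.

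**Inputs from the documents.** Eight delays in 20 ms steps from 220 to 80 ms; selection by the largest averaged VTI; 20 cycles per step; 40 patients; significance level 0.05 (two-sided assumed).

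**Sweep length.** 8 × 20 = 160 cycles. At 70 bpm, 160 × 60/70 = 137 s, about 2.3 min. At 90 bpm, 160 × 60/90 = 107 s, about 1.8 min. Reprogramming and imaging time are extra.

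**Delay selection.** Reading at step k (k = 0 to 7) = true VTI + drift × k/7 + error, all in percent of VTI, with error SD 3% or 5%. The true response is either flat or curved: loss = 4% × ((delay − 150)/70)². The delay with the largest reading is chosen. With no drift the mean chosen delay is 150 ms. Shift in the mean when the delays run from 220 down to 80 ms:

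| Total drift | Flat, SD 3% | Flat, SD 5% | Curved, SD 3% | Curved, SD 5% |
|---|---|---|---|---|
| -1% | 8 ms | 5 ms | 4 ms | 3 ms |
| -3% | 23 ms | 14 ms | 12 ms | 10 ms |
| -6% | 40 ms | 27 ms | 23 ms | 19 ms |

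Upward drift shifts the mean the other way. A random order per patient gives 150 ms in every row. So does the descending order when the drift sign varies at random between patients, although individual choices are still disturbed.

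**Cost of the shifted choice.** In the curved case, mean true VTI at the chosen delay, as a percentage of the peak, descending against random order:
- SD 3%, drift -3%: 99.11 against about 99.16; drift -6%: 98.86 against 99.09.
- SD 5%, drift -3%: 98.87 against 98.90; drift -6%: 98.74 against 98.87.

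The loss due to order is 0.03 to 0.23 percentage points. In the flat case it is zero by construction.

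**AAI versus DDD.** Assume no true difference, n = 40, one fixed order, and a signed-rank test at two-sided 0.05 (assumed, since the SAP names no test for this contrast). As a rough check, the expected standardized shift is shift/(SD/√40). For a 2% shift and a paired-difference SD of 5% it is 2/(5/6.32) = 2.53, which implies rejection in about 70% of trials. Simulated false-positive rates:
- 2% shift: 0.70 at SD 5%, 0.24 at SD 10%.
- 5% shift: 1.00 at SD 5%, 0.85 at SD 10%.
- No shift: 0.049.

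With 20 patients in each order, the bias is about zero and the rate lies between 0.002 and 0.049.

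**Separate selection bias.** If the DDD value used is the winning sweep reading itself, it is biased upward. The expected maximum of eight independent standard normal values is about 1.42. With a flat response and no drift, that gives 1.42 × 3% = 4.3% and 1.42 × 5% = 7.1%. The size is the same in either test order, so random order alone does not remove it.

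**The case against.** The strongest objection is that the plan does not prescribe the order being criticized. A reader might infer that delays are tested in descending sequence and modes in a fixed sequence, so that drift is an established confounder. The text supports neither. Section 9 lists the delays and the conditions to be compared, with no word on sequence. AAI could be recorded after the sweep, because only optimized DDD has to wait for it. This objection stands: the defect is an unspecified order, and the confounding is conditional.

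Three further points also stand. First, a mean shift needs drift with a common sign, and the plausible causes have no obvious shared direction. Second, millisecond shifts overstate the consequence: the largest ones arise where the response is flat and the choice of delay costs nothing. With a steeper curve (8% loss at the ends), -3% drift moves the mean by only about 6.5 ms. Third, paced time per sweep is about two minutes, so drift within it may be small.

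The 20-cycle wait does not answer the concern. It deals with carry-over from the previous setting, not with a trend across the session. The interval from an initial AAI reading to optimized DDD also spans at least the whole sweep.

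A reader might also infer that the 6-month result is compromised. It is not: that comparison is between arms, and session drift does not confound it. At most, the delay programmed in one arm is shifted.

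**Conclusion.** The concern holds as a conditional risk and is a low-priority improvement. The protocol leaves the test order open and gives no protection against time trends in a comparison that relies on patients as their own controls. Bias follows only if conditions are tested as listed, AAI is recorded once before the sweep, and drift has a common direction across patients.

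For delay selection the practical loss is small, about 0.2 percentage points of true VTI or less under the curved response assumed. The Aim 1 contrast is more exposed: an assumed 2% shift between conditions would give a false-positive rate of 0.24 to 0.70. Whether a shift of that size occurs cannot be judged from the documents.

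**What to change.** In section 9, state that the eight AV delays are tested at each rate in a random order generated per patient, and record that order. After the optimum is chosen, re-record AAI and optimized DDD at each rate in random order. Specify that these fresh readings, not the sweep values, are used for the acute comparison. The fresh DDD reading also avoids the largest-of-eight bias. In the SAP, name the paired analysis for this contrast. If sessions have already taken place, report the order actually used and whether the DDD value came from the sweep.

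The cost is a printed order per patient and about two further 20-beat recordings per rate. Paced time is 2 × 20 × 60/70 = 34 s at 70 bpm and 2 × 20 × 60/90 = 27 s at 90 bpm, plus reprogramming and imaging. No extra staff or visit is needed.

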Patients will then be randomized in a 1:1 ratio by order of enrollment to either the echocardiographically optimized AV interval or to a long-fixed AV delay that will allow for intrinsic conduction. Patients will have routine clinical follow up at 3 month intervals in the pacemaker clinic as per our usual standard of care, and then will have a comprehensive follow up 2D echo at 6 months after randomization to assess for any potential changes related to RV pacing including, RV function, LV function, LV end-systolic volume, LV end-diastolic volumes, wall thickness, and dyssynchrony as assessed by tissue Doppler imaging.

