DIVISION OF CARDIOVASCULAR MEDICINE
[contact]
NIGHTS & WEEKENDS: [contact]
[contact]

OFFICE OF:
[name].
PROFESSOR OF MEDICINE
DIRECTOR EP PROGRAM
[name]
[name]
[contact]

Date: November 15, 2024

To: Whom it may Concern

Re: Project # 130663
NCT02154750

Evaluation of AV Delay Optimization vs. Intrinsic Conduction in Patients with Long PR Intervals
Receiving Dual Chamber Pacemakers for Symptomatic Bradycardia.

Statistical Analysis Variables are displayed as the mean \pm 1SD. Categorical variables are presented as number and percentage. For comparisons of the baseline categorical variable between groups, chi-square test was used. Wilcoxon signed-rank test was used to compare each variable between baseline and 6 months after randomization. The change in each parameter was compared between each group using the Mann-Whitney U test. A p value of < 0.05 was considered statistical significance. Analyses were performed using SPSS version 23 (IBM corporation, Chicago, Illinois).

If there are any questions or concerns regarding this submission, please contact [name], Research Coordinator, at [contact]. Thank you for your consideration in this matter.

Sincerely,

A handwritten signature in black ink, appearing to read "[name]".

[name] /bb
Professor of Medicine
Director Cardiac Electrophysiology Program
University of California, San Diego

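### Averaging only three to four beats at each AV delay, with no respiratory control stated, leaves avoidable noise in the choice of delay and in the acute VTI values

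*Protocol*

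**What the plan says.** The Methods part of Protocol section 9 sweeps aortic Doppler VTI "at eight AV intervals: 220, 200, 180, 160, 140, 120, 100, 80 ms". The averaging rule is: "After 20 cardiac cycles at each AV delay, measurements will be made on the final three to four cardiac cycles and averaged". The selection rule is: "The optimal AV delay will be defined as the AV delay associated with the largest average aortic Doppler VTI".

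The result is used twice:
- **Acute comparison.** AAI pacing at two rates is compared "with DDD pacing 70 bpm and 90 bpm at the optimal AV delay achieved with atrio-ventricular pacing at each heart rate".
- **Assigned setting.** "Patients will then be randomized in a 1:1 ratio by order of enrollment to either the echocardiographically optimized AV interval", or to a long fixed delay that allows intrinsic conduction. The follow-up echocardiogram is at 6 months.

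Neither document mentions breath-hold, end-expiratory acquisition, a repeat sweep, curve fitting or a minimum VTI difference between delays. The three-to-four-cycle rule is written for the AV delays, and no window is stated for AAI. The protocol does not say whether VTI is measured again at the chosen delay. The SAP does not address VTI averaging or repeatability.

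**The concern.** A mean over a few beats carries two errors. One is beat-to-beat and tracing noise, which shrinks only with the square root of the number of beats. The other is respiratory swing in stroke volume, which does not average out when the window covers only part of a breath and the phase differs between delays. Picking the largest of eight such means favours whichever delay happened to be measured high.

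Two things could suffer. The chosen delay may not be the best of the eight. And if the VTI from the selecting sweep is also the DDD value set against AAI, that value is biased upward, while AAI is not selected in this way. In section 10 the protocol states that "A total of 40 patients will be recruited", about 20 per arm, so avoidable measurement noise is worth removing where it is cheap to do so.

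**Working it through.** The documents give no figure for VTI precision or repeatability, so there is nothing to reproduce.

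**Inputs from Protocol section 9:** 3 to 4 beats; 70 and 90 bpm; eight delays, 80 to 220 ms in 20 ms steps; largest mean wins.

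**Assumed inputs (not in the documents):** 12-18 breaths/min; sinusoidal respiratory swing with amplitude A of 0 to 5% of VTI and a random phase at each delay; beat-to-beat SD 3%; quadratic VTI curve losing 10% at 100 ms from the optimum; true optimum at 120, 140, 160 or 180 ms.

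**Step 1. Window length** = beats × 60 / bpm.
- 70 bpm: 3 × 60/70 = 2.6 s; 4 × 60/70 = 3.4 s.
- 90 bpm: 3 × 60/90 = 2.0 s; 4 × 60/90 = 2.7 s.
- Ten beats: 8.6 s at 70 bpm, 6.7 s at 90 bpm.
- One breath: 60/18 = 3.3 s to 60/12 = 5.0 s.

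Every three-to-four-beat window is shorter than one breath, except four beats at 70 bpm above 17.5 breaths/min.

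**Step 2. Share of the swing left in a k-beat mean** = |sin(kx) / (k sin x)|, with x = π × breaths per min / bpm.

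| 15 breaths/min | 3 beats | 4 beats | 10 beats |
|---|---|---|---|
| 70 bpm | 48% | 17% | 7% |
| 90 bpm | 67% | 43% | 17% |

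Over 12-18 breaths/min the share runs from 3% to 78% with 3-4 beats and from 0% to 21% with ten.

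**Step 3. Error SD of one mean** = √(3²/k + (A × share)²/2), in % of VTI.
- Best case, 4 beats, no respiratory part: √(9/4) = 1.5%.
- Worst case, 3 beats, 90 bpm, 12 breaths/min, A = 5: √(9/3 + (5 × 0.78)²/2) = √(3.0 + 7.6) = 3.3%.
- Ten beats, no respiratory part: √(9/10) = 0.95%.
- Ten beats, same worst case: √(0.9 + (5 × 0.21)²/2) = √(0.9 + 0.55) = 1.2%.

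**Step 4. Choosing the largest of eight** (simulation, 20,000 patients per setting; ranges over the assumed inputs).

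| Result | 3-4 beats | 10 beats |
|---|---|---|
| Chosen delay 40 ms or more off | 14-29% | 6-10% |
| Exact optimum chosen | 26-36% | 39-43% |
| Mean true VTI lost | 0.4-0.8% | 0.3-0.4% |
| Selected mean overstates that delay's own VTI by | 1.6-3.9% | 0.9-1.2% |

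With respiration set to zero, three to four beats still give 14-18% at 40 ms or more off. On this curve a 20 ms miss costs 10 × (20/100)² = 0.4% of VTI and a 40 ms miss 10 × (40/100)² = 1.6%.

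**Step 5. Sensitivity.** Vary the curve (2-20% loss at 60 ms) and the amplitude (2.5-7.5%) at 15 breaths/min. Respiration alone then makes the choice differ from the best of the eight in 0-75% of patients, and by 40 ms or more in 0-33%. The mean true VTI lost is 0-1.1%. Beat noise of 3% alone gives 23-74% misses of any size. In a middle case (5% loss at 60 ms, 5% amplitude, 3% noise), averaging 10-12 beats lowers such misses from 61-69% to 48-51%. If the true optimum may lie between candidate delays and error is counted from it, the 40 ms rate in Step 4 becomes 5-15% against 1-3%.

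**The case against.** A reader might infer that breathing determines the choice, that the optimized arm is often away from its optimum, and that the 6-month comparison is weakened. The case against that reading is strong, and most of it stands.

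- **Breathing is not the main driver under these inputs.** With no respiratory swing the 40 ms miss rate is still 14-18%. If the laboratory acquires at held expiration, which is possible but not written, the respiratory part disappears.
- **The word often is not established.** The rate depends on the swing, the beat noise and the curve shape. The documents give none of these, and Step 5 shows how wide the range is.
- **Misses are cheap in VTI.** Rates are highest where the curve is flat, and there the wrong delay is nearly equivalent to the right one.
- **The 6-month contrast is about RV pacing burden.** Entry requires a PR interval above 230 ms and all candidate delays are 80-220 ms. Section 7 of the protocol expects substantial ventricular pacing at physiologic intervals. A shift of 20-40 ms within that range leaves the patient in the high-pacing arm.
- **The unmeasured earlier cycles serve a purpose.** They can be read as run-in after a change of delay, so tracing them would reintroduce beats that the protocol leaves out.

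What the objection does not remove is the measurement rule itself. A two-to-three-second window with no stated respiratory control is noisier than it needs to be, from both sources, and a largest-of-eight rule turns that noise into upward bias.

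**Conclusion.** The point holds as one of measurement precision. Beat noise and respiratory swing can both influence which delay is called optimal, and both add noise to the acute VTI values. Under the stated assumptions, ten beats instead of three to four reduce the error SD of each mean from about 1.5-3.3% to 0.95-1.2%, and selections 40 ms or more off from about 14-29% to 6-10%. The overstatement of the selected mean falls from about 1.6-3.9% to 0.9-1.2%. That last gain reaches the AAI comparison only if the sweep value is reused there, which the protocol leaves open.

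The documents do not support attributing the problem to breathing alone, or a claim that the 6-month contrast is materially weakened. This is a cheap improvement of lower priority. Confidence is high for the window arithmetic and low for the exact rates, which rest on assumed inputs.

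**What to change.** In Protocol section 9, Methods, keep the 20-cycle run-in at each setting and then average at least 10 consecutive cycles (8.6 s at 70 bpm, 6.7 s at 90 bpm). State that the same window applies to baseline, AAI and every DDD setting at both rates. Also state whether VTI is re-measured at the chosen delay for the comparison with AAI.

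Three to four beats at held end-expiration is not an equivalent alternative, because it removes the respiratory part and leaves the beat noise.

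Cost: about 7-9 s more recording per setting. If the eight-delay sweep is run at both rates, nine settings per rate (eight delays plus AAI) add 9 × 8.6 + 9 × 6.7 ≈ 138 s, plus baseline. Tracing takes a few more minutes per patient. No extra visit or procedure is needed.

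The SAP is written in the past tense. If recording is already complete, report the number of beats and the respiratory phase used, and re-trace longer windows where the stored recordings allow. That can improve the acute values but cannot change the delays already assigned.

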6. SPECIFIC AIMS

To evaluate the acute effects on cardiac output with a long AV delay allowing for intrinsic conduction as compared to an echocardiographically optimized AV delay during dual chamber pacing, and then to follow the patients to see if there are any remodeling changes related to a high degree of RV pacing.

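### The protocol does not say whether the DDD VTI compared with AAI is the same measurement that selected the AV delay; if it is, the acute comparison is biased on average toward optimized DDD

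*Protocol*

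**What the plan says.** Section 6 of the protocol puts the acute question first: "To evaluate the acute effects on cardiac output with a long AV delay allowing for intrinsic conduction", compared with an echo-optimized delay. Section 9 makes the comparison within patient: "thus patients will serve as their own controls with respect to the acute hemodynamic data".

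The Methods part of section 9 then sets out these steps.

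- **Comparison.** Aortic VTI at baseline and under AAI pacing at 70 and 90 bpm is set against VTI "with DDD pacing 70 bpm and 90 bpm at the optimal AV delay achieved with atrio-ventricular pacing at each heart rate".
- **Sweep.** "Measurement of continuous-wave aortic Doppler flow velocities in the apical five chamber view at baseline and at eight AV intervals", from 220 down to 80 ms in steps of 20 ms. After 20 cycles at each delay, "measurements will be made on the final three to four cardiac cycles and averaged".
- **Selection.** "The optimal AV delay will be defined as the AV delay associated with the largest average aortic Doppler VTI".
- **Further imaging.** "Measurements of diastolic dysfunction and dyssynchrony will also be re-evaluated with AAI pacing and with DDD pacing at optimized AV delays".

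The SAP describes no acute analysis. It assigns the signed-rank test to baseline versus 6 months and the Mann-Whitney test to between-group change. It gives no VTI variability.

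**The concern.** The same VTI average may serve twice: once to pick the delay and again as the result at that delay. The largest of eight noisy averages tends to be one whose error happened to be positive. AAI has one setting per rate and is not selected, so nothing offsets this. An apparent gain with optimized DDD could then be partly an artefact of selection, and a true loss with RV pacing could be hidden. Since the optimum is found separately at each rate, both the 70 and the 90 bpm contrasts would be affected.

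At stake is the interpretation of the first specific aim. As the plan is written, a reader could not tell how much of an acute benefit comes from choosing the highest value.

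**Working it through.** **What the text permits.**

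| Point in section 9 | New DDD measurement | Sweep value reused |
|---|---|---|
| AAI and DDD at the chosen delay are listed as parallel conditions | fits | fits |
| AAI is not in the sweep, so it must be recorded separately | fits | fits |
| After selection both modes are imaged again, and the sentence says *also* | suggests VTI may be included | VTI is not named there |
| The sweep is the only described acquisition of DDD VTI, and it includes the baseline value | not excluded | fits |

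No sentence settles the matter.

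**Direction if the sweep value is reused.** Let the observed average at delay *j* be Y_j = m_j + e_j, with m_j the true VTI and e_j an error of mean zero. Then E[max Y_j] ≥ max m_j, with strict inequality whenever error can change the ranking. The AAI average has expectation equal to its true value. The difference DDD minus AAI is therefore too high on average.

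**Size.** The plan states no figure to reproduce. From the documents: 8 delays, 3 to 4 beats, 40 patients, significance at p < 0.05. Assumed: normal errors with equal variance. The unit *s* is the SE of one averaged VTI, counting only error that is independent between delays.

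1. Flat curve (all m_j equal): bias = E[max of 8 standard normals] = ∫ x·8·φ(x)·Φ(x)^7 dx = 1.42 *s*. This is the largest case.
2. Peaked curve: an assumed quadratic with its peak at 160 ms (illustration only), falling by D·*s* over 80 ms. From 400,000 simulated sweeps:

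| D | Bias against true VTI at the chosen delay | Bias against the true best delay |
|---|---|---|
| 0 | 1.42 *s* | 1.42 *s* |
| 1 | 1.36 *s* | 1.15 *s* |
| 2 | 1.26 *s* | 0.99 *s* |
| 4 | 1.08 *s* | 0.78 *s* |
| 8 | 0.89 *s* | 0.57 *s* |

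3. Shared error: if a fraction ρ of the total error variance is common to all eight averages, *s* = √(1−ρ) × total SE. For a flat curve the bias is 1.42 × √0.5 = 1.01 total SE at ρ = 0.5, and 1.42 × √0.2 = 0.64 at ρ = 0.8.
4. Percent of VTI, if per-beat CV is 5–10% (assumed) and all error is beat-to-beat: *s* runs from 5%/√4 = 2.5% to 10%/√3 = 5.8%. The flat-curve bias is then 1.42 × 2.5% = 3.6% up to 1.42 × 5.8% = 8.2%. For D = 8 it is 0.89 × 2.5% = 2.2% up to 0.89 × 5.8% ≈ 5.1%.

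**Effect on a test, as illustration only.** This assumes a two-sided paired signed-rank test at 0.05, n = 40, and AAI truly equal on average to the best DDD value. The between-patient SD of the true difference (τ) is 2 or 4 *s*. In 2,000 simulated trials per case, reuse gave significant results favouring DDD in 95% and 56% (flat) and in 53% and 21% (D = 4), against a nominal 2.5%. At τ = 7 the flat case falls to about 23%. With a new measurement and a flat curve the rates were 2.8% (τ = 2) and 2.4% (τ = 4).

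**The case against.** The strongest case against is that the harmful interpretation is only one of two. Section 9 brings the patient back to both modes at the chosen delay for further imaging, and its wording fits VTI being recorded then. The absence of a separate description of DDD VTI acquisition proves little, because AAI acquisition is not described separately either and must take place. All of this stands. A reader might infer that the plan calls for a biased analysis, or that the acute result is biased; the documents support neither.

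The second objection is to the rates, and it also stands. The SAP names no acute test, and the measurement error, curve shape, shared error and τ are all assumed. A reader might take the high rates as the trial's actual false-positive risk. They belong to a flat curve with independent errors and a modest τ, and they fall quickly outside those conditions.

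A reader might also suspect the randomized results. Each arm there is compared on 6-month echo measures, and the sweep value is not the outcome. A delay chosen with error is part of the strategy under test, so no selection bias follows.

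What remains is that reusing the winning value would comply with the plan as written, and that the direction of the resulting bias does not depend on the assumed sizes.

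**Conclusion.** The concern holds in conditional form. The plan leaves open which DDD VTI enters the acute comparison. If it is the selecting one, the comparison favours optimized DDD on average; if it is a new one, this bias is absent. The direction is firm wherever error can alter the ranking of delays. The size is not knowable from the documents. At most it is 1.42 times the independent SE of one averaged VTI, for a flat curve under normal, equal-variance errors, and it shrinks with a more peaked curve or when more of the error is shared. Any false-positive rate is illustrative. The point is worth correcting because it touches the first specific aim and the remedy is small.

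**What to change.** **Protocol, section 9.** State that the eight-delay sweep is used only to choose the delay. At each rate, record new VTI beats in DDD at the chosen delay, with the same 20-cycle wait and the same number of beats as for AAI. Only these enter the paired acute comparison. The new value is unbiased for the delay actually chosen.

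**Cost.** The added DDD wait is 20 × 60/70 + 20 × 60/90 = 17.1 + 13.3 ≈ 30 seconds, plus reprogramming and acquisition. AAI is recorded separately anyway, so its wait is not an extra cost. The reported acute benefit may be smaller.

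**If recording is complete**, as the SAP's past tense and its heading ("Date: November 15, 2024") suggest:

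- Report which DDD measurement was analysed. If it was a new one, that sentence closes the point.
- If it was the selecting one, state that the acute benefit is biased upward on average.
- Optionally, if sweep averages at both rates were kept, add a cross-rate sensitivity analysis: DDD VTI at 90 bpm at the delay chosen at 70 bpm, and the reverse. It has no selection bias if errors in the two sweeps are independent. It understates DDD on average if the optimum differs by rate. With an assumed curve falling 5 SE over 80 ms, the understatement is 5 × (20/80)² = 0.31 SE for a 20 ms shift and 5 × (40/80)² = 1.25 SE for a 40 ms shift. It is therefore a conservative check and not a replacement estimate.
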